8.7 Investigational Product Accountability

It is the responsibility of the Principal Investigator to ensure that the current disposition of the Investigational Product is maintained at each study site where Investigational Product is inventoried and dispensed. When a drug shipment is received at a study site, the Principal Investigator or the Principal Investigator's designee must inventory the drug and sign the receipt form provided with the shipment. The receipt form should be emailed as per instructions provided on the receipt. A copy of the receipt should remain at the site.

The Investigator will not supply study test articles to any person not enrolled in this study, or to any physician or scientist except those named as sub-Investigators.

A Drug Accountability Log will assist study site staff in maintaining inventory records of study drug.

Subjects must return used, partially used or unused Investigational Product so that any remaining drug supplies can be accounted for and noted in the Drug Accountability Log.

A certified copy of the Drug Accountability Log will be collected by the study monitor at the conclusion of the study and the original should remain at the study site.

8.8 Return of Clinical Supplies

All used and unused containers of Investigational Product may be returned to the Drug Labeling, Packaging and Shipping Facility for destruction or be destructed at the site after study close-out and final drug accountability is reconciled.

9. STATISTICAL METHODS

9.1 Scientific and Statistical Considerations of the Study Design

[REDACTED]

9.1.1 Rationale for the Selected Subject Population

Randomization and re-randomization will be stratified by gender and prior biologic therapy for psoriasis. Approximately the same number of male and female subjects will be enrolled between treatment groups. A maximum of [REDACTED] of randomized subjects may have prior exposure to biologics therapy for psoriasis. Approximately the same number of subjects who have prior exposure to biologics therapy for psoriasis will be enrolled between treatment groups.

Subjects with conditions or treatments that may affect cardiovascular safety (e.g. heart rate less than [REDACTED], history of uveitis or history of pulmonary conditions such as active severe respiratory disease (e.g. COPD, tuberculosis or pulmonary fibrosis, severe asthma or asthma requiring regular treatment with oral steroids) will be excluded due to the known mechanism-based AEs within this class which may expose such subjects to unwarranted excess risk for a condition with available alternatives.

9.1.2 Rationale for Dose Selection

The image consists of a series of horizontal black bars of varying lengths, arranged in a grid-like pattern. The bars are set against a white background. The first and last bars are the longest, while the middle bars are shorter. The bars are evenly spaced both horizontally and vertically.

© 2013 Pearson Education, Inc.

A series of eight horizontal black bars of varying lengths, decreasing in length from left to right. The bars are evenly spaced and extend across the width of the frame.

9.1.4 Rationale for the Use of Comparator

A placebo control arm is included to demonstrate that the investigational products are active and as a

parameter that the study is sufficiently sensitive to detect differences between products.

9.1.5 Rationale for Study Endpoints

The primary end-point will be the proportion of subjects with at least a 75% improvement in Psoriasis Area and Severity Index (PASI75) at Week 16. Duration of 16 Weeks is considered adequate to detect a clinically meaningful difference between placebo and active treatment and is consistent with previous studies in this indication. Proportion of subjects achieving Investigator's Global Assessment (IGA) of "clear" or "almost clear" with at least a two-grade reduction from baseline to Week 16 will be a key secondary end-point. It is anticipated that only a limited proportion of randomized patients will meet baseline criteria for assessment of efficacy in scalp psoriasis, nail psoriasis, psoriatic arthritis and palmar plantar psoriasis. Hence assessments of efficacy in these subsets are designated as tertiary end-points.

9.1.6 Rationale for the Overall Study Design

[REDACTED]. The primary and key secondary endpoints are based on efficacy assessments at Week 16 (end of Part 1). The study involves evaluation of efficacy and safety over a longer duration of up to 52 weeks. This long term evaluation comprises Parts 2 and 3 of the study.

9.3 Blinding and Unblinding Procedures

In order to maintain the study blind the randomization schedule will be generated by a third party. Randomization will be performed according to a computer-generated randomization scheme. The placebo and tablets for all strengths of SCD-044 look alike which ensures blinding. The Investigational Product will be identically labeled and packaged such that neither the Subject nor any Investigator can identify the treatment. The Drug Labeling, Packaging and Shipping facility will hold the randomization code throughout the conduct of the study to minimize bias. A sealed copy of the randomization scheme (as a scratch off portion of the product label attached to the drug accountability page) will be retained at the study site. In the event of an emergency, the Subject-specific treatment may be identified; however, every effort should be made to maintain the blind. Where possible, the Medical Monitor should be

Confidential

contacted before breaking the blind for any subject. The Sponsor must be notified in the event the blind is broken.

The treatment assignments will remain blinded until the final database is closed.

[figure not shown]
The following safety professionals will be allowed to be unblinded as necessary on a case by case basis:

-
-
-
-

If SUSAR requires unblinding by a Regulatory Agency, a designated member of the Sponsor's safety team will be un-blinded on case-by-case basis by receiving the randomization directly from the study unblinded statistical consultant.

9.4 Significance Level

Tests for superiority over placebo for the primary and the key secondary endpoint will be conducted using a hierarchical closed testing step-down approach to preserve the overall Type I error rate of 0.05.

0.05. 

9.5 Datasets to be analyzed

Three analysis populations will be used in the analysis of the clinical data:

1. A Safety Population subject is any individual who was randomized into the study and dispensed study drug.
2. The ITT Population includes all randomized subjects regardless of whether they received the investigational product.
3. The Per Protocol (PP) Population includes all ITT subjects who meet all inclusion/exclusion criteria and have no protocol violations that affect proper administration of the treatment or accurate evaluation of its effectiveness.

Additionally, the Screen Fail subjects will be summarized, including reasons for removal.

9.6 Demographics and Baseline/Randomization Characteristics

Demographic and baseline/randomization characteristics will be summarized descriptively by treatment group for the ITT, PP, and Safety Populations.

9.7 Safety Assessment

Safety Assessments will include vital signs, physical examination, adverse events (AEs), laboratory tests, ECG monitoring, pulmonary function tests, ophthalmologic exams.

The safety of SCD-044 will be evaluated by:

- Incidence, seriousness and severity of all adverse events
- Shifts from baseline in hematology and laboratory tests
- Incidence of AEs of special interest (AE-SI)
- [REDACTED]
- [REDACTED]

The extent of exposure will be summarized using descriptive statistics. No inferential analyses are planned.

Incidence of all adverse events reported during the study will be summarized using the MedDRA dictionary by System Organ Class and Preferred Term, by treatment group, severity, and relationship to study drug.

An AE is considered treatment emergent if it was not present prior to the first dose of treatment or, if it was present, it worsened in severity or treatment attribution.

Safety analyses will be performed on the Safety Population. All safety data will be listed by treatment and subject in data listings. AEs will also be summarized by actual dose at time of onset of the AE to account for possible dose reductions over the course of the study.

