### **6.1.1 Treatment Groups**

Data collected up to Week 16 visit will be analyzed by treatment groups based on the subject’s treatment in Part I of the study:

- Placebo

- SCD-044 [REDACTED]
- SCD-044 [REDACTED]
- SCD-044 [REDACTED]

Efficacy data collected after Week 16 visit (i.e., Parts II-IV), as well as disposition and compliance in Parts II-IV, will be analyzed by treatment groups based on the responder status at the end of Part I (Week 16) (i.e.,  $\geq$  PASI50 or  $<$  PASI50), the subject's treatment in Part I and the subject's treatment in Part II of the study:

- Part I Responders
  - Placebo/SCD-044 [REDACTED]
  - Placebo/SCD-044 [REDACTED]
  - SCD-044 [REDACTED]
  - SCD-044 [REDACTED]
  - SCD-044 [REDACTED]
- Part I Non-Responders
  - Placebo/SCD-044 [REDACTED]
  - Placebo/SCD-044 [REDACTED]
  - SCD-044 [REDACTED]
  - SCD-044 [REDACTED]

Safety data collected after Week 16 visit (i.e., Parts II-IV) will be analyzed by treatment groups based on the subject's treatments in Part I and in Part II:

- Placebo/SCD-044 [REDACTED]
- Placebo/SCD-044 [REDACTED]
- SCD-044 [REDACTED]

Adverse events and concomitant medications will be additionally analyzed for the entire study. Details are provided in the sections 6.11.1 and 6.11.6.

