### **6.11.1 Adverse Events**

Adverse events will be coded using MedDRA, Version 25.0, AE coding system for purposes of summarization.

An AE will be considered as treatment-emergent (TEAE) if the date of onset is on or after the date of the first study drug administration. AEs with unknown start dates will be counted as treatment-emergent unless the AE resolution date is prior to the study drug start date. If the start date is partially missing, the AE will be considered treatment-emergent, unless the month and year (when available) rule out the possibility that the event occurred post start of study drug dosing.

A TEAE is defined as treatment-related if its relationship to study medication is recorded as “Possible”, “Probable” or “Definite” on the eCRF. In case the relatedness was not assessed, the most conservative result (related) will be chosen for the analysis.

Cardiovascular AEs will be defined as AEs with MedDRA system organ class “Cardiac disorders” or “Vascular disorders”.

Adverse events that are of special interest, that represent signs/symptoms of Progressive Multifocal Leukoencephalopathy (PML) or of Posterior Reversible Encephalopathy Syndrome (PRES) and that are cardiac arrhythmias will be marked on the eCRF.

AEs will be assigned to Part I or Parts II/III of the study based on the date of onset, i.e. AEs that start prior to the first dose of the Part II treatment will be assigned to the Part I and AEs that start on or after the date of the first Part II dose will be assigned to the Parts II/III. In case AE start date is partially known so that there exists an ambiguity whether the AE starts in Part I or Part II, it will be assigned to Part I.

In summaries of TEAEs a subject experiencing the same AE multiple times on the same treatment will only be counted once for that preferred term and treatment. Similarly, if a subject experiences multiple AEs within the same system organ class on the same treatment that subject will be counted only once in that system organ class and treatment. When summarizing AEs by severity, only the most severe occurrence within the preferred term or system organ class and treatment will be used. Similarly, when summarizing AEs by relationship to study drug, only the most related occurrence within the preferred term or system organ class and treatment will be selected for displays in summary tables.

All AE summaries will be presented in 3 ways:

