1. For events in Part I only, using Part I treatment groups, with the additional groups SCD-044 Any Dose (including the three SCD-044 groups) and Total (including all subjects).
2. For events in Parts II/III/IV only, using Parts II/III/IV safety treatment groups, with the additional group Total.

3. For the entire study using only the subjects who stayed on the same treatment throughout the study, using the three active treatment groups with the additional group Total.

An overall summary for the Safety population will include, by treatment and overall, the number and percentage of subjects reporting at least 1 TEAE in the following categories:

- Any TEAE
- Treatment-related TEAE
- Serious TEAE
- Serious drug-related TEAE
- TEAE leading to discontinuation of the study medication
- Treatment-related TEAE leading to discontinuation of the study medication
- TEAE requiring temporary interruption of the study medication
- Treatment-related TEAE requiring temporary interruption of the study medication
- TEAE leading to death.
- TEAEs of special interest

Additional overall summary of cardiovascular TEAEs will include, by treatment and overall, the number and percentage of subjects reporting at least one cardiovascular TEAE in the following categories:

- Any cardiovascular TEAE
- Treatment-related cardiovascular TEAE
- Serious cardiovascular TEAE
- Cardiovascular TEAE leading to discontinuation of the study medication
- Cardiovascular TEAE leading to death.
- Cardiovascular TEAEs of special interest
- Cardiac arrhythmias

The following TEAE frequency tables will be prepared summarizing the number and percentage of subjects reporting at least one TEAE by MedDRA System Organ Class (SOC) and preferred term PT, by treatment group for the Safety population:

- All TEAEs
- Serious TEAEs
- Treatment-related TEAEs
- Serious treatment-related TEAEs
- TEAEs leading to discontinuation of the study medication
- Treatment-related TEAEs leading to discontinuation of the study medication
- TEAE requiring temporary interruption of the study medication
- Treatment-related TEAE requiring temporary interruption of the study medication
- TEAEs occurring in  $\geq 2\%$  in any treatment group
- TEAEs of special interest
- Cardiac arrhythmias
- TEAEs with onset during the [REDACTED] period in Part I and in Part II
- TEAEs by Severity

- TEAEs by Relationship to Study Drug.

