### **8. CHANGES FROM PROTOCOL SPECIFIED ANALYSES**

Handling of intercurrent events is expanded in this SAP.

The endpoint of achieving DLQI score of 0 or 1 was added.

There are no other changes from the protocol-specified analyses.

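### The protocol promises an AE summary by actual dose at onset; SAP 6.11.1 does not plan one, SAP 8 does not declare the omission, and the only whole-study AE table is limited to subjects who never switched

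*Protocol*

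**What the plan says.** Protocol section 9.7 first describes AE incidence by treatment group, severity and relationship. It then adds, without condition, that "AEs will also be summarized by actual dose at time of onset of the AE"; the reason it gives is that doses might be reduced during the study.

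SAP section 6.11.1 says "All AE summaries will be presented in 3 ways". These are:

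1. Early events by initial group: "For events in Part I only, using Part I treatment groups". An any-dose column and a total over all subjects are added.
2. Later events by treatment sequence: "For events in Parts II/III/IV only, using Parts II/III/IV safety treatment groups, with the additional group Total".
3. A whole-study view restricted to non-switchers: "For the entire study using only the subjects who stayed on the same treatment throughout the study". Its columns are the three active groups plus a total.

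SAP section 6.1.1 defines the groups used in the second presentation: "Safety data collected after Week 16 visit (i.e., Parts II-IV) will be analyzed by treatment groups based on the" pair of treatments the subject had in Part I and in Part II.

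SAP section 8 names two departures from the protocol (fuller handling of intercurrent events, and an added DLQI endpoint) and closes with "There are no other changes from the protocol-specified analyses".

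**The concern.** This is a dose-ranging study with a titration schedule and a Week 16 reallocation that depends on PASI response. A subject's dose on the day an event starts can therefore differ from the label of the assigned group: during titration, around missed doses or interruptions, and after any reduction. The protocol planned a summary that follows the dose actually in force. If the SAP is followed as written, that summary will not be produced, and a reader of section 8 would not know it had been planned.

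The whole-study table cannot take its place. Low and Intermediate subjects are moved to High dose according to their Week 16 response. Those who move leave the table altogether, and their Part I events leave with them. The SAP's account of who changes treatment (section 6.1, Part II baseline) names placebo subjects and subjects from two active doses, so the High column is not thinned by switching. Comparing AE percentages across the columns of that table would therefore mix dose with response.

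**Working it through.** No figure in the plan needs reproducing. The check is a comparison of text, followed by two short calculations.

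**Step 1. The commitment against the three presentations.**

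| SAP 6.11.1 presentation | Subjects | Columns | By dose at onset? |
|---|---|---|---|
| 1. Part I | All Safety subjects | Part I group | No |
| 2. Parts II/III/IV | All who continue | Part I/Part II sequence | No |
| 3. Entire study | Non-switchers only | Three active groups | No |

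**Step 2. Does another part of the SAP supply it?**

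- The tables of events in the early dosing period (SAP 6.11.1) are split by week, for three weeks in each of Part I and Part II. Their columns are still treatment groups, and they cover only those weeks and the groups still in that period.
- Repeat events are collapsed within subject and treatment, not within dose.
- The fields named for the AE listing do not include dose at onset, so the summary cannot be rebuilt from that listing alone.
- SAP 6.7.1 derives total and average daily dose, but takes tablet strength from the schedule. It gives no rule for the dose on a particular date.

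None of these is the summary in protocol 9.7.

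**Step 3. Coverage of the whole-study table.** Inputs: about 240 subjects allocated 1:1:1:1 (protocol 4.1). Continuing placebo subjects move to active drug, and Low and Intermediate subjects may move to High (protocol section 3). Let s be the share of Low and Intermediate subjects who switch; the visible text does not give it.

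- Per arm: 240 / 4 = 60.
- Placebo: no column, so 60 are outside.
- Active: 3 × 60 = 180, of whom Low plus Intermediate are 2 × 60 = 120.
- Covered: 180 − 120s.
- s = 0: 180 of 240 = 75%.
- s = 1: 180 − 120 = 60 of 240 = 25%.

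This uses the randomised number in place of the Safety Population, and counts active subjects who stop early without switching as still in the table.

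**Step 4. Why a dose-at-onset table needs person-time.** Part I lasts 16 weeks. Parts II and III run from Week 16 to Week 52, with dosing stopped at Week 28 for subjects below PASI75 (protocol section 3 and the Week 28 visit, section 7.1.9).

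- A non-switcher who completes spends 52 weeks in one dose group.
- A switcher spends 16 weeks in the first dose group, then 28 − 16 = 12 weeks or 52 − 16 = 36 weeks in the next.

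Titration shortens time at the assigned dose further, by amounts that are redacted. Plain percentages by dose would compare groups observed for very different lengths of time.

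**The case against.** Much can be said for the SAP as it stands.

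- **Events are not lost.** A reader might infer that switchers' AEs disappear, or that no AE table includes them. The SAP does not support that. Presentations 1 and 2 together count all Safety subjects' treatment-emergent events by period, and the sequence labels show the dose group assigned at the time. This stands. The gap is confined to attribution by dose at onset and to a whole-study table for everyone.
- **Titration is partly handled.** Under a fixed schedule, group and week together identify the scheduled dose, and the early-period tables provide that split. This stands for those weeks and for subjects who keep to the schedule. It does not give the dose actually in force after a missed dose or interruption, and it does not pool events at the same dose across groups.
- **The protocol's stated reason is narrow.** It names dose reductions, not titration or the Week 16 switch. Protocol 4.7 says that subjects whose treatment must be interrupted for their health, or for factors that disturb the study, should be withdrawn rather than kept on an altered regimen. Reductions may therefore be uncommon and the missing summary may differ little from the planned tables. This limits the weight of the point. Interruptions remain, since the SAP plans tables of events that require temporary interruption.
- **The table may exist elsewhere.** The shells are in a separate document (SAP section 9) that was not available for this review. That is possible, but the SAP text does not call for the table.
- **Version difference.** The SAP introduction cites protocol 4.1 and the protocol reviewed is 4.2. The 4.2 entries in the revision history list no change to section 9.7, so this does not appear to explain the omission.

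**Conclusion.** The point holds in a limited form. A safety summary that the protocol promises without condition is absent from the SAP, and the closing statement of SAP section 8 is wrong on this item. The only whole-study AE table covers 60 to 180 of about 240 subjects, has no placebo column, and has Low and Intermediate columns selected on Week 16 response. The range is wide because the switch rate is not given; it rests on equal arms of 60 and the counting assumptions stated with the calculation.

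Two stronger readings should be resisted. A reader might infer that long-term AE rates will come mainly from responders because of this choice. That describes the whole-study table, but the Parts II/III/IV presentation also includes re-randomised placebo subjects and subjects switched to High dose. Selection at Week 28 comes from the design and would remain in any table, including the one proposed here. A reader might also infer that half the subjects are missing from the whole-study table. That needs a 50% switch share (180 − 120 × 0.5 = 120 of 240), which is an assumption and not a figure in the documents.

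The primary and key secondary efficacy analyses are unaffected. The practical effect on the safety picture may be modest if few subjects depart from the scheduled dose.

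**What to change.** Add a fourth presentation to SAP 6.11.1: treatment-emergent AEs by actual dose at onset, for all Safety subjects across all parts, with placebo and each titration dose as separate categories. Specify with it:

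- **A rule for the dose on the onset date.** It should use recorded interruptions and any recorded reductions, because the scheduled strength assumed in SAP 6.7.1 would not capture them. It should also say how partial onset dates, days without drug and events after the last dose are assigned.
- **Person-time at each dose as denominator**, with rates per subject-year beside the counts. Neither document promises this in its visible text; it is needed because time at each dose differs.

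Keep the whole-study table of non-switchers if wanted, with a footnote that its Low and Intermediate columns are selected on Week 16 response.

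Correct SAP section 8 to record the added denominator and derivation rule. If the sponsor prefers to drop the summary, section 8 should list and justify its removal. Settle this before the Part I outputs described in SAP 7.3 are produced.

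The cost is one new derived variable with its rule, and one extra descriptive table set. If reductions are few, the new tables may add little beyond the planned ones.
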